### 15.5 Adherence to the Protocol

The study must be conducted as described in the approved protocol. Any significant deviation from the protocol must be reported immediately to the Sponsor and IEC.

## 15.6 Protocol Amendment

Any amendment to the protocol will be created by the Sponsor, and subsequently submitted by the site to the IEC and appropriate regulatory authority for approval.

## 15.7 Retention of Patient Records

When the study is completed, the investigators must retain the essential documents for as long as needed to comply with regulatory guidelines and Sponsor requirements. The investigators will notify the Sponsor prior to moving or destroying any of the study documents.

The Sponsor will maintain the data collected (study database) for at least 5 years.

## 16 PLANS FOR DISSEMINATING AND COMMUNICATING STUDY REPORT

The Sponsor and/or designee will develop a final study report after the end of the study. Results will be posted on Clinical Trials.gov.

This study is intended for publication, even if terminated prematurely. Publication may include any or all of the following: posting of a synopsis online, abstract and/or presentation at a scientific conference, or publication of a full manuscript. Authorship credit will follow the guidelines established by the International Committee of Medical Journals Editors and, as such, should be based on the following criteria 1) substantial contributions to the conception or design of the work; or the acquisition, analysis, or interpretation of data for the work; 2) drafting the work or revising it critically for important intellectual content; 3) final approval of the version to be published and 4) agreement to be accountable for all aspects of the work in ensuring that questions related to the accuracy or integrity of any part of the work are appropriately investigated and resolved. All authors must meet all above criteria. Although publication planning may begin before conducting the study, final decisions on authorship and the order of authors' names will be made based on participation and actual contributions to the study and writing, as discussed above.

## APPENDICES

None

**3.0 LIST OF ABBREVIATIONS**

AESI	adverse event of special interest
BCVA	best-corrected visual acuity
CI	confidence interval
eCRF	electronic case report form
EDC	electronic data capture
CNV	choroidal neovascularization
CRT	central retinal thickness
DME	diabetic macular edema
DV	derived variable
ETDRS	early treatment diabetic retinopathy study
IOP	intraocular pressure
OCT	optical coherence tomography
OD	oculus dexter (right eye)
OS	oculus sinister (left eye)
OU	oculus urteque (both eyes)
PT	preferred term
SAP	statistical analysis plan
SD	standard deviation
SOC	system organ class
VEGF	vascular endothelial growth factor

## **4.0 INTRODUCTION**

This statistical analysis plan (SAP) provides a more technical and detailed elaboration of the statistical analyses of the real-world utilization, effectiveness and safety data as outlined in the final protocol of Study CMO-MA-EYE-0564 (version dated 24 JUL 2018). Specifications of tables, figures, and data listings are contained in a separate document.

### Study design

[figure not shown]
Study CMO-MA-EYE-0564 is a retrospective, non-interventional, observational, multi-center, drug utilization study to be conducted in adult patients with visual impairment due to DME treated with Ozurdex implants in Germany and Switzerland from 1 January 2015 to 1 September 2018. Data from approximately 150 patients will be collected by retrospective review of medical charts; including up to 50 patients that are naïve of any anti-VEGF treatment before their first Ozurdex implant injection. Sites will be hospital-based experienced medical retina centers treating DME patients.

[figure not shown]
Patients' medical charts will be selected over a 4-month period at each site or until the study target population has been reached. Site personnel will be invited to complete a screening log with all patients who received their first Ozurdex implant injection from 1 January 2015 until 1 September 2017 to help them identify eligible patients. For each patient, retrospective data on the study eye will be abstracted from existing medical records from time of first Ozurdex implant injection until 1 September 2018. Data abstraction will cover at least one year of follow-up after first Ozurdex injection for all selected patients. The study eye will be defined as the eye that received the most Ozurdex injections. Key relevant data will also be collected on the contralateral eye.

Consent from patients will not be requested; as the study is retrospective and anonymized, a waiver of consent will have been requested from the Ethics Committees.

### Study assessments

The schedule of assessments for Study CMO-MA-EYE-0564 is presented in Table 4-1.

### Sites and study population

Site selection will aim to recruit qualified ophthalmologists experienced in intravitreal injections who are most likely to treat patients with DME with Ozurdex. A sample of ophthalmologists working in experienced medical retinal centers treating DME patients will thereby be selected.

From a public health and market access perspective, the present study population constitutes a broader real-world patient population than that reflected in clinical trials. The present study design cannot make any conclusions on causal relationships, but can rather explore real-world Ozurdex drug utilization patterns, effectiveness and safety. It is expected that the results from this study may be generalizable to the overall population presenting with DME and treated with Ozurdex in Germany and Switzerland.

Patients may contribute at most one eye into the study. If both eyes meet the inclusion and exclusion criteria, the eye that received the most Ozurdex injections will be chosen as the study eye.

Inclusion criteria are:

1. Patient received at least two Ozurdex implants in the study eye to treat visual impairment due to DME

2. Male or female patient aged  $\geq 18$  years at time of first Ozurdex implant injection in the study eye
3. First Ozurdex implant injection in the study eye occurred after 1 January 2015
4. Patient was followed-up at the site for at least 12 months after the first Ozurdex implant injection in the study eye

Exclusion criterion is:

1. Patient received Ozurdex implants in the study eye as part or during a clinical study

[REDACTED]

[REDACTED]

[REDACTED]

## **5.0 OBJECTIVES**

### Primary objective

The primary objective of this study is to assess reinjection interval of Ozurdex implants in patients with DME in real-world in Germany and Switzerland.

### Secondary objectives

The secondary objectives of this study are:

- To assess the relationship between reinjection intervals and drug effectiveness
- To describe the reasons for reinjection
- To assess drug effectiveness in patients who are naïve of any anti-VEGF treatment
- To present those adverse events of special interest (AESIs) that may be potentially related to Ozurdex injection

## **6.0 PATIENT POPULATIONS AND SUBGROUPS**

### **6.1 ELIGIBLE SCREENING LOG POPULATION**

All patients from the screening log who meet selection criteria will be considered in the Eligible screening log population.

As a reminder, site personnel will be invited to complete a screening log with all patients who received at least one Ozurdex implant injection to help them identify eligible patients. Based on data recorded in the screening log, a patient will be considered as meeting selection criteria if s/he meets all the criteria below:

- The number of Ozurdex implant injections is  $\geq 2$  in at least one eye.
- Patient's age at first Ozurdex implant injection is  $\geq 18$  years old
- Date of the first Ozurdex implant injection is  $\geq$  January 2015
- Time from the first Ozurdex implant injection to the most recent follow-up visit prior to 01 September 2018 [DV] is  $\geq 365$  days.
- 'Patient received Ozurdex implants as part or during a clinical trial' is equal to 'No'

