Data Collection Procedures	
The following data concerning patient treatment and clinical condition will be collected at the indicated time points.
 
Screening Log
 
 
• Ozurdex injected to treat visual impairment due to DME
 
• Number of Ozurdex implant injection in each eye
 
• Patient's age at first Ozurdex implant injection
 
• Date (MM YYYY) of first Ozurdex implant injection
 
• Date (MM YYYY) of last follow-up visit
 
• Anti-VEGF injections before first Ozurdex implant injection
 
• Patient received Ozurdex implants as part or during a clinical study
 
• Reason why the patient has not been selected for the study, if applicable
 
 
Case Report Form
 
Relevant data will be collected at baseline, defined as the period prior to first Ozurdex implant injection (index event), and during the study period, defined as the period between the first Ozurdex implant injection and 1 September 2018.
 
 
• Demographics at baseline (age and gender)
 
• Medical and Ophthalmic history (chronic medical conditions and medical conditions ongoing at time of first Ozurdex implant injections, glaucoma, cataract, and lens status)
 
• Prior and concomitant treatments in the study eye (prior and concomitant cataract and glaucoma procedures, prior and concomitant laser therapy, prior and concomitant intravitreal injections other than Ozurdex [including but not limited to anti-VEGF injections], concomitant medications)
 
• Clinical examinations in the study eye (intraocular pressure measurement, biomicroscopic and ophthalmomicroscopic exams performed)
 
• Contralateral eye information (DME status, treatments for DME received prior and during the study period)
 
• BCVA in both eyes at baseline and during the study period
 
• CRT measured in the study eye at baseline and during the study period
 
• Ozurdex implant injections in the study eye during the study period (date of injections and, if available, reason for initial injection and for reinjections)
 
• AESIs: glaucoma, intraocular hypertension, hypotony, cataract or lens
 

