## 5 INTRODUCTION

### 5.1 Background

Ozurdex® is a biodegradable solid polymer drug delivery system containing 0.7 mg of dexamethasone. A single-use applicator with a 22-gauge needle that leaves a sutureless self-sealing wound is used to place the dexamethasone implant into the vitreous cavity. The sustained-release formulation was designed to release dexamethasone from the implant for up to 6 months. Ozurdex was granted a marketing authorization in the European Union in 2010 for the treatment of adult patients with macular edema following vein occlusion. In 2011, Ozurdex was furthermore approved for treatment of adult patients with inflammation of the posterior segment of the eye presenting as non-infectious uveitis. More recently, in 2014, Ozurdex was approved for treatment of adult patients with visual impairment due to diabetic macular edema (DME) who are pseudophakic or who are considered insufficiently responsive to, or unsuitable for non-corticosteroid therapy.

DME is a common manifestation of diabetic retinopathy; diabetic retinopathy being microvascular abnormalities seen in the fundus of persons with diabetes. In most studies, DME is defined by hard exudates in the presence of microaneurysms and blot hemorrhages, resulting in increased central retinal thickness (CRT) within one disc diameter of the foveal center. Clinically significant macular edema is the most severe spectrum of DME, and was defined by the presence of edema within 500 µm of the foveal center, or focal photocoagulation scars present in the macular area. The prevalence of DME in population-based studies among type-1 diabetes patients varied between 4.2% and 7.9%. In patients with type-2 diabetes it was between 1.4% and 12.8%. DME is a leading cause of serious central visual loss impairment in diabetic patients. Due to worldwide rise of diabetes mellitus and of life expectancy of those with diabetes mellitus, burden of illness of microvascular complications, such as DME, is expected to increase over time.

Clinical evaluation of DME may be difficult and subjective. Gold standard for DME diagnostic still remains the fluorescein angiography, but optical coherence tomography (OCT) can be used for screening, classification, monitoring, and treatment evaluation of the DME. It has the ability to provide information on CRT as well as distinct morphological features of the edema.

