### **6.2 ANALYSIS POPULATION**

The Analysis population will consist of all selected patients for whom an eCRF have been completed and who meet selection criteria (See Section 4.0).

All analyses described in this SAP will be performed on the Analysis Population, unless otherwise specified.

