## **8.0 PHYSICIAN AND PATIENT DISPOSITION**

Physician disposition will be summarized overall and by country using descriptive statistics for the following parameters: number of solicited, responding, participating and active physicians, number of non-participating physicians and reason for non-participation, and number of patients included per physician. The number of physicians who returned the Screening logs will also be described.

Patient disposition will be summarized overall and by country using descriptive statistics for the following parameters: number of patients recorded in screening logs, number of patients in the Eligible screening log population and reason for exclusion, number of included patients, number and percentage of patients in the Analysis population and reason for exclusion, number of follow-up visits per patient, dates of the first and last date of the first Ozurdex injection in the study eye, date of the last follow-up visit and study duration (months) [DV] for patients from the Analysis population.

The proportion of patients from the Eligible screening log population actually included in the study will also be calculated using the variable '*Chart entered in EDC (Yes/No)*' from the Screening log. This proportion will enable to assess the representativeness of patients included in the study compared to patients not included.

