## **9.0 DESCRIPTION OF THE ELIGIBLE SCREENING LOG POPULATION**

Analysis will be performed overall and:

- by inclusion in the study (Yes vs. No). It is to be noted that due to patient anonymization it will not be possible to link patients listed in the screening log and patients included in the study; the number of patients included according to the screening log ('Chart entered to EDC=Yes') may not match with the number of patients actually included in the study according to eCRF. The variable 'Chart entered to EDC' from the screening log will be used to distinguish both of these groups.
- by reason for non-inclusion in the study (Did not meet selection criteria, Lack of time, Quotas were met, Other)

Characteristics of patients of the Eligible screening log population will be summarized using descriptive statistics for the following variables collected in the screening log: age at first Ozurdex implant injection (years), gender, anti-VEGF injections before the first Ozurdex implant injection (Yes, No), number of Ozurdex implant injections in each eye.

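### SAP 6.1 omits the DME indication from the Eligible screening log population, so non-DME Ozurdex patients can count as eligible but not included in SAP 8.0 and 9.0

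*SAP*

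**What the plan says.** SAP 6.1 draws the Eligible screening log population from log patients who meet the selection criteria and then defines that test: "Based on data recorded in the screening log, a patient will be considered as meeting selection criteria if s/he meets all the criteria below". The list has five entries:

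- at least two implants in at least one eye
- age 18 or over at first implant
- first implant in January 2015 or later
- at least 365 days of follow-up
- no implant received in a clinical trial

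The list shows no redaction.

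Inclusion criterion 1 asks for more than a count. In SAP 4.0, and in the same words in Protocol 8.2.1, it reads: "Patient received at least two Ozurdex implants in the study eye to treat visual impairment due to DME".

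The log is limited by date, not by indication. SAP 4.0 describes "a screening log with all patients who received their first Ozurdex implant injection from 1 January 2015 until 1 September 2017", and SAP 6.1 itself refers to everyone with at least one implant. The synopsis of the protocol lists, as the first log item, "Ozurdex injected to treat visual impairment due to DME".

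Two outputs rest on this population. SAP 8.0: "The proportion of patients from the Eligible screening log population actually included in the study will also be calculated"; that section reads the result as a measure of representativeness. SAP 9.0 describes the population by inclusion (yes or no) and also "by reason for non-inclusion in the study (Did not meet selection criteria, Lack of time, Quotas were met, Other".

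**The concern.** SAP 6.1 keeps the implant count from inclusion criterion 1 and drops the indication. Other indications exist. Protocol 5.1 states that "Ozurdex was granted a marketing authorization in the European Union in 2010 for the treatment of adult patients with macular edema following vein occlusion", and adds non-infectious uveitis in 2011.

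A patient with two or more implants for either condition can pass all five rules and still be properly excluded from the study. Under the written rule that patient is labelled eligible but not included.

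Protocol 7.3.1.2 and SAP 7.0 rely on comparing selected with non-selected patients to judge selection bias. The SAP 9.0 comparison covers age, gender, prior anti-VEGF use and number of implants. Protocol 5.1 ties the DME approval to pseudophakia, or to poor response to or unsuitability for non-corticosteroid therapy, and describes the other two uses without that condition. Prior treatment could therefore differ by indication, and the difference could be misread as selection bias within DME.

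**Working it through.** The plan gives no figure for this point, so there is none to reproduce. The check compares the texts and then illustrates the size.

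**Step 1. Which criteria the log can test, and which SAP 6.1 applies.**

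| Element of the selection criteria | Log item in Protocol synopsis | Applied in SAP 6.1 |
|---|---|---|
| Implants given for DME | yes | **no** |
| Two or more implants | yes | yes |
| Age 18 or over | yes | yes |
| First implant from January 2015 | yes | yes |
| 12 months of follow-up | yes | yes |
| No implant in a clinical study | yes | yes |

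The indication is the only one of these left out. SAP 22.0 does not declare it as a change from the protocol.

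**Step 2. Whether a later step removes these patients.** SAP 9.0 says log patients cannot be linked to eCRF patients, so the indication cannot be recovered from the eCRF. It is not among the variables SAP 9.0 summarises. The table of reasons for non-inclusion can show some of these patients, but neither the SAP 8.0 proportion nor the yes/no comparison sets that group aside.

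**Step 3. Whether the objectives are touched.** They are not. SAP 6.2 says: "The Analysis population will consist of all selected patients for whom an eCRF have been completed and who meet selection criteria (See Section 4.0". Those criteria include DME.

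**Step 4. Illustration of size.** Let I be patients included, E the DME patients passing the five rules, and N the non-DME patients passing them.

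- Reported proportion = I / (E + N)
- Non-DME share of the not-included group = N / (E − I + N)

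I = 150 is the target in SAP 19.0, taken as all DME. E and N are assumptions; the documents give neither.

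| E | N | Proportion | Non-DME share of not-included |
|---|---|---|---|
| 200 | 0 | 150/200 = 75.0% | 0/50 = 0% |
| 200 | 20 | 150/220 = 68.2% | 20/70 = 28.6% |
| 200 | 50 | 150/250 = 60.0% | 50/100 = 50.0% |
| 200 | 100 | 150/300 = 50.0% | 100/150 = 66.7% |
| 400 | 0 | 150/400 = 37.5% | 0/250 = 0% |
| 400 | 20 | 150/420 = 35.7% | 20/270 = 7.4% |
| 400 | 50 | 150/450 = 33.3% | 50/300 = 16.7% |
| 400 | 100 | 150/500 = 30.0% | 100/350 = 28.6% |

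The relative fall in the proportion is N / (E + N). The non-DME share of the not-included group has the smaller denominator E − I + N, so for any N above zero the comparison group is affected more than the proportion.

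**The case against.** Four points can be made in defence of the plan.

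1. **The reason table isolates most of these patients.** Everyone in this population has already passed the five rules. Those recorded as failing the selection criteria must therefore mainly fail on indication, on a redacted additional exclusion, or on a detail that month-level dates cannot resolve. Their count could be subtracted by hand. This is real mitigation, but the SAP does not plan the subtraction, the group is not split by criterion, and the pooled medians and quartiles cannot be corrected that way.

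2. **The opening sentence of SAP 6.1 refers to the selection criteria in general, which include DME.** The omission may be a slip. The explicit list follows immediately, however, and a programmer will code the list.

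3. **The final log is not visible.** The content of Protocol 10.1 is redacted, and SAP 8.0 and 9.0 use log variables that the synopsis does not list (gender, chart entered in EDC). The DME item may not have survived, or the log may have been limited to DME. This stands: contamination is possible but not shown. A DME item in the planned log does suggest that a DME-only log was not intended.

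4. **The outputs are descriptive and ancillary, and the illustrated size rests on assumptions.** Both are true. With a larger pool of DME patients the effect shrinks, which is why E is varied as well as N.

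**Conclusion.** The point holds. The rule in SAP 6.1 is not just short on detail: followed literally, it classes patients who fail inclusion criterion 1 as eligible. They then lower the SAP 8.0 proportion and mix indication into the pooled SAP 9.0 comparison, the two outputs meant to show whether selection was representative.

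The size cannot be determined. It is zero if no non-DME patient was logged. Over the assumed values above (E of 200 or 400, N from 20 to 100), the proportion is understated by 1.8 to 25.0 percentage points, and non-DME patients form 7.4% to 66.7% of the not-included group. The reinjection-interval, effectiveness and AESI analyses do not change. It should be fixed; confidence is medium because the final log cannot be seen.

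**What to change.** Add a sixth rule to SAP 6.1: the log item "Ozurdex injected to treat visual impairment due to DME" must equal Yes. In the SAP 8.0 disposition, count patients who fail it under the reasons for exclusion from the Eligible screening log population.

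If the final log was restricted to DME patients, say so in SAP 6.1 instead.

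The cost is one line of specification and one filter in the program, or one sentence. Provided the DME item is in the final log, as the protocol synopsis lists it, no new data and no link to the eCRF are needed.

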### **6.2 ANALYSIS POPULATION**

The Analysis population will consist of all selected patients for whom an eCRF have been completed and who meet selection criteria (See Section 4.0).

All analyses described in this SAP will be performed on the Analysis Population, unless otherwise specified.

### **6.3 SUBGROUPS**

The following subgroups will be considered for analysis:

- Treated with Ozurdex in Switzerland vs. Germany
- Patients who are naïve of any anti-VEGF treatment in the study eye prior to the first Ozurdex injection in the study eye: Yes vs. No [DV].
- Number of anti-VEGF treatments in the study eye prior to the first Ozurdex injection in the study eye: 0, 1 to 3, 4 to 6,  $>6$  [DV].
- Lens status of the study eye during the study period: Phakic throughout vs. Pseudophakic throughout vs. Change from Phakic to Pseudophakic [DV].

- At least one concomitant treatment with anti-VEGF and/or corticosteroids in the study eye: Yes vs. No [DV]

Table 6-1 presents subgroups that will apply for each analysis.

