### 14.2.1 Study Populations and Analysis Methods

- Analysis Population: data will be summarized for all patients who were selected and met the selection criteria.
- Subgroups analysis will be conducted in patients who are naïve for anti-VEGF treatment. If the sample size allows it, analyses will also be conducted in a subgroup of patients who received 6 or less anti-VEGF treatments prior to the first Ozurdex implant injection.
- Additional groups also may be examined, as deemed appropriate such as according to lens status at baseline (phakic vs. pseudophakic) or according to concomitant treatments (concomitant anti-VEGFs vs. Ozurdex only).

Continuous variables will be described by their mean, SD, median, first and third quartiles, extreme values (minimum and maximum) and the number of missing data.

Categorical variables will be described by the total and percentage of each response and the number of missing data.

Two-sided 95% CI of the mean and of percentage may also be calculated when appropriate. Data may also be presented graphically when relevant.

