**Table 6-1 Planned Subgroup Analyses**

Analysis	Subgroups				
Demographics and other baseline characteristics (Section 10.0)	X	Treated with Ozurdex in Switzerland vs. Germany	Patient naïve to anti-VEGF in the study eye prior to the 1 st Ozurdex injection in the study eye: Yes vs. No	Number of anti-VEGF treatments in the study eye prior to baseline: 0, 1 to 3, 4-6, >6	Lens status of the study eye during the study period: Phakic throughout vs. Pseudophakic throughout vs. Change from Phakic to Pseudophakic
Diabetes and DME status (Section 11.0)	X				X
Clinical examination in the study eye (Section 12.0)	X				
Prior and concomitant treatments and surgeries (Section 13.0)	X				
Primary objective (Section 15.1)	X	X	X	X	X
First secondary objective (Section 15.2.1)	X	X	X	X	X
Second secondary objective (Section 15.2.2)	X	X	X		X
Third secondary objective (Section 15.2.3)					
Fourth secondary objective (Section 15.2.4)	X				

The planned subgroup analysis specified in Table 6-1 above may not be performed if the number of patients in the subgroup is too small.

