## **15.0 ANALYSES OF THE OBJECTIVES OF THE STUDY**

### **15.1 ANALYSIS OF THE PRIMARY OBJECTIVE**

The primary objective '*To assess reinjection interval of Ozurdex implants in patients with DME in real-world in Germany and Switzerland*' will be assessed by the following outcomes:

- Total number of Ozurdex reinjections in the study eye during follow-up, and considering years after the first Ozurdex injection in the study eye (See definition in Table 21-1).
- Re[injection interval defined in months as: (Date of injection (j+1) – Date of injection j) ÷ (365.25÷12), for j=1,...,n where n is the number of reinjections in the study eye. The result will be rounded to 0.1.

The number of Ozurdex reinjections in the study eye per year will be first summarized using descriptive statistics for the following parameters:

- The total number and percentage of Ozurdex reinjections received during follow-up.
- Number and percentage (with 95% CI) of patients with at least one Ozurdex reinjection during Year 1 (See definition in Table 21-1), and number of reinjections per patient during Year 1, for all patients in the analysis population. Note: the first Ozurdex injection will not be considered here, only reinjections will be counted.
- Number and percentage (with 95% CI) of patients with at least one Ozurdex reinjection and number of reinjections per patient during Year k (k=2, 3), for patients having a complete Year k of follow-up (see definition of 'Complete year' in Section 21.2).
- Number and percentage of patients receiving each Ozurdex reinjection (first, second, third, etc) for each year of follow-up (Year k, k=1 to 3) considering patients having the complete year of follow-up.

The Ozurdex reinjection interval in the study eye will be described using descriptive statistics for the following parameters:

- Re[injection interval (months) considering all eligible reinjections recorded in the EDC. The 95% CI of the mean will also be presented.
- Re[injection interval (months) considering each reinjection separately (i.e. first reinjection, second reinjection, etc). 95% CI of the mean will also be presented.

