### **21.3.3 Variables Related to Lens Status**

#### At least one change in lens status in the study eye during the follow-up period

Using information from eCRF section '*Biomicroscopy – Lens – Study eye*' (BIL/F8 form), the variable will be derived to:

- Yes, if the variable '*1.0 - Have there been any changes to lens status in the study eye to report at this visit?*' is equal to 'Yes' in at least one follow-up visit
- No, if the variable '*1.0 - Have there been any changes to lens status in the study eye to report at this visit?*' is equal to 'No' at all follow-up visits available for the patient
- Missing, if the variable '*1.0 - Have there been any changes to lens status in the study eye to report at this visit?*' is equal to 'Not in Chart' in at least one follow-up visit and is never equal to 'Yes' at the other follow-up visits.

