## **22.0            CHANGES TO ANALYSES SPECIFIED IN PROTOCOL**

The changes to the analyses specified in the original protocol, dated 24 July 2018, are specified below:

In protocol Section 14.2.2.3.2 it is specified that reason of initial injection and for reinjection will be described. Reason for initial injection is not collected in the eCRF and therefore only reason for reinjection will be described.

No analyses will be performed on the contralateral eye with the exception of AESIs (Section 15.2.4) and select measures of ophthalmic history and current ophthalmic conditions (Section 10.2).

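### The SAP's lens subgroup is defined by events during follow-up, so total reinjections will be higher in the 'change' group simply because those patients are followed longer

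*SAP*

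**What the plan says.** - **Protocol 14.2.1:** "Additional groups also may be examined, as deemed appropriate such as according to lens status at baseline (phakic vs. pseudophakic". This is an option, and the lens state it names is the one at baseline.
- **SAP 6.3:** the only lens subgroup is "Lens status of the study eye during the study period: Phakic throughout vs. Pseudophakic throughout vs. Change from Phakic to Pseudophakic". Table 6-1 is broken in the extracted text, but the rows for the primary and first secondary objectives are marked in all five positions, so lens status is included however the columns are read.
- **SAP 21.3.3:** the underlying variable is "At least one change in lens status in the study eye during the follow-up period", taken over all follow-up visits the patient has.
- **SAP 15.1:** the first primary outcome is "Total number of Ozurdex reinjections in the study eye during follow-up", with no allowance for length of follow-up. Year 1 reinjections are reported for everyone, and Years 2 and 3 only "for patients having a complete Year k of follow-up".
- **SAP 22:** "The changes to the analyses specified in the original protocol, dated 24 July 2018, are specified below". Two items follow, on the reason for initial injection and on the contralateral eye. The lens subgroup is not among them.

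**The concern.** Membership of the 'change' group is settled after baseline. Of two phakic eyes with the same risk of surgery, the one observed longer is more likely to have its surgery recorded, and it also has more time to collect reinjections. Comparing total reinjections between 'phakic throughout' and 'change' therefore compares short with long follow-up. The protocol requires at least 12 months and allows data from 1 January 2015 to 1 September 2018, so follow-up can differ by a factor of about 3.7. Protocol 5.1 says cataract events in the phase III trials became more frequent after the first year, which ties being seen to change still more closely to long observation.

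The table for the primary objective could then show more reinjections in eyes whose lens changed, and a reader could take this as an effect of the lens when treatment was the same.

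**Working it through.** **The plan's own figure.** The documents give no figure for the lens subgroup. The nearest yardstick is the precision of the mean interval, ω = 1.96 × SD / √n with n = 150:

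- SD 1.5: 1.96 × 1.5 / 12.247 = 0.24 months.
- SD 3.0: 1.96 × 3.0 / 12.247 = 0.48 months.

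This agrees with the stated 0.2 to 0.5 months.

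**Inputs from the documents.** Minimum follow-up is 12 months. The maximum is 1339 days / 30.4375 = 43.99 months. Interval means run from 4.7 to 6.7 and SDs from 1.5 to 3.0 months (SAP 19.0).

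**Assumptions.** All eyes are phakic at baseline and have the same gamma-distributed intervals. At least one reinjection is required. Follow-up F is uniform on (a, b). Surgery has a constant hazard h that does not depend on injections. The documents give no surgery hazard. For cataract-related events, 67.9% over 3 years gives −ln(1 − 0.679) / 36 ≈ 0.032 per month, so h = 0.01 to 0.04 was used for surgery.

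**Step 1: follow-up by group.** The share that stays phakic is S = [e^(−ha) − e^(−hb)] / [h(b − a)]. Mean follow-up in that group is [(a + 1/h)e^(−ha) − (b + 1/h)e^(−hb)] / [e^(−ha) − e^(−hb)]. The mean in the change group follows from the overall mean (a + b)/2. For a = 12, b = 43.99, h = 0.02:

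- S = (0.7866 − 0.4149) / (0.02 × 31.99) = 0.581.
- Phakic throughout: (62 × 0.7866 − 93.99 × 0.4149) / 0.3718 = 26.3 months.
- Change: (27.995 − 0.581 × 26.3) / 0.419 = 30.3 months.

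The gap is about 4.0 months. At one injection per 5.5 months that is 4.0 / 5.5 ≈ 0.73 extra reinjections.

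**Step 2: simulated totals, follow-up uniform over 12–44 months.**

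| Interval mean/SD | h per month | Phakic throughout | Change | Excess |
|---|---|---|---|---|
| 5.5/2.0 | 0.01 | 4.49 | 5.14 | 14% |
| 5.5/2.0 | 0.02 | 4.35 | 5.08 | 17% |
| 5.5/2.0 | 0.04 | 4.06 | 4.98 | 23% |
| 4.7/1.5 | 0.04 | 4.79 | 5.88 | 23% |
| 6.7/3.0 | 0.01 | 3.66 | 4.19 | 14% |

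In the second row 5.08 − 4.35 = 0.73, as in Step 1.

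**Step 3: longer follow-up.** Protocol 9.2 has sites select consecutively from the first injections nearest 1 January 2015, which lengthens potential follow-up. A slightly different model was used here: surgery at 2% per month after month 6, and interval mean 5.8 with SD 1.3 between and 1.6 within patients.

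- 24–44 months: 5.64 v 5.91, and 5.91 / 5.64 = 1.05.
- 32–44 months: 6.43 v 6.52, and 6.52 / 6.43 = 1.01.

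At h = 0.04 over 24–44 months, the Step 1 formula gives mean follow-up of 32.68 v 34.47 months. The ratio is 1.055, so the upper end is nearer 6%.

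**Step 4: outcomes with a fixed window (5.5/2.0, h = 0.02, 12–44 months).**

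| Outcome | Phakic throughout | Change |
|---|---|---|
| Year 1 reinjections | 1.75 | 1.75 |
| Complete Year 2 | 2.18 | 2.19 |
| Complete Year 3 | 2.19 | 2.18 |
| Reinjections per patient-year | 1.99 | 2.01 |
| Mean interval, months | 5.33 | 5.36 |

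The interval gap of 0.03 months is far below the 0.24 to 0.48 yardstick. With every patient followed for exactly 24 months, total reinjections are 3.93 in both groups.

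**Step 5: surgery that depends on injections.** The Step 3 interval model was used with follow-up over 12–44 months.

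| Hazard per month per injection | Year 1 | Complete Year 2 | Mean interval, months |
|---|---|---|---|
| 1% | 1.61 v 1.81 | 2.05 v 2.25 | 5.64 v 5.21 |
| 0.5% | 1.65 v 1.84 | 2.12 v 2.28 | 5.53 v 5.14 |

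Here patients who are injected more often are sorted into 'change'.

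**The case against.** Much of the case against stands. The fixed-window counts already planned in SAP 15.1 show no artefact, and the interval, which is what the primary objective names, barely moves. The size of the effect on totals depends on a follow-up distribution that the documents do not give. Consecutive selection from January 2015 favours the lower figures, although last visits may fall before the cut-off and anti-VEGF-naïve patients are selected separately. The study is descriptive, tests no hypothesis, disclaims causal conclusions and may drop small subgroups. Separating eyes whose lens changed is also a reasonable thing to want for visual acuity.

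Three stronger readings are tempting, and the documents do not support them.

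- **That follow-up time biases every reinjection count and the interval.** Step 4 shows that it does not. The differences in Step 5 need surgery to be driven by injections. The phase III figures in Protocol 5.1 (67.9% v 20.4% with sham) make this plausible, but it is a separate concern: grouping on a consequence of exposure. The gap then reflects a real difference in injection frequency between the groups.
- **That the SAP breaks a protocol commitment.** The protocol's wording is permissive, so the silence of SAP 22 is a point of transparency.
- **That BCVA results by lens group are shown to be biased.** In 'change' eyes, BCVA change from baseline can span cataract surgery, which mixes lens replacement with drug effect. No size was calculated for this.

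One qualification runs the other way. SAP 21.2 also ends follow-up at the first concomitant anti-VEGF or corticosteroid, yet defines a complete year by the last visit. The SAP does not say whether Year-k counts are cut in the same way. If counts and lens changes both are, Year 1 would differ too: 1.57 v 1.72 to 1.31 v 1.66 at h = 0.02 with assumed concomitant-treatment hazards of 0.01 to 0.03 per month.

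**Conclusion.** The concern holds for total reinjections during follow-up. Under equal treatment, that total is higher in 'change' than in 'phakic throughout' because of follow-up length alone. The excess is 14–23% if follow-up is uniform over 12–44 months and h is 0.01 to 0.04 per month. It is about 1–5% if follow-up is concentrated in 24–44 or 32–44 months (h = 0.02; near 6% at 0.04). The direction does not depend on these assumptions as long as follow-up varies and surgery is unrelated to treatment pattern; the size does.

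If counts run to the last visit, Year 1 counts, complete Year 2 and 3 counts and the interval are essentially unaffected by follow-up length. This is a modest defect in one descriptive comparison, and it is worth correcting because the correction costs almost nothing.

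**What to change.** 1. In SAP 6.3 and Table 6-1, use baseline lens status (phakic v pseudophakic) as the subgroup for the primary and effectiveness objectives. State where aphakic eyes go, since SAP 12.1 allows that category.
2. Keep the throughout/change classification as a descriptive table under SAP 12.1. SAP 21.3.3 should derive the three-level variable, which it does not do at present.
3. If that classification stays in the primary analysis, read it only on Year-k counts or on reinjections per patient-year, and not on total reinjections. State whether the SAP 21.2 end-of-follow-up rule applies to the counts, and end the person-time at the same point.
4. For BCVA, show lens status at each injection as a supplement.
5. Note the choice of lens subgroup in SAP 22.

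The cost is SAP wording and a little programming. Baseline lens status is already collected and tabulated, and changes are recorded by visit. The drawback is that the baseline phakic group mixes eyes with and without later cataract surgery; item 4 makes that visible for BCVA.
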